8.3.5. Physical Examinations

Physical examination will be listed.

8.4. Pharmacokinetics Evaluation

Summaries of concentrations, PK parameters and statistical analysis for unchanged edaravone, sulfate conjugate, and glucuronide conjugate will be performed using data from subjects whose PK data will be available in at least one treatment.

8.4.1. Concentrations and Pharmacokinetic Parameters for unchanged edaravone, sulfate conjugate, and glucuronide conjugate

Plasma unchanged edaravone, sulfate conjugate, and glucuronide conjugate concentrations will be summarized at each nominal sampling point for each treatment. All plasma concentrations will also be listed.

For each treatment, individual plasma concentrations vs. actual time for unchanged edaravone, sulfate conjugate, and glucuronide conjugate will be plotted on both linear/linear and log/linear scales. Mean plasma concentrations vs. nominal time curves will be plotted on both linear/linear (+SD) and log/linear scales overlaid by each treatment.

The PK parameters listed in Section 2.2.2 will be calculated for each subject using non-compartmental model. The PK parameters will be listed and summarized by each treatment. The PK parameters listed as other PK parameters will not be summarized. The urinary pharmacokinetic parameters will be listed and summarized for each treatment. The urinary pharmacokinetic parameters at pre-dose will not be summarized.

8.4.2. Analysis of Food Effect

The parameters C_{max} , $AUC_{0-\infty}$, AUC_{0-24} , and AUC_{0-t} of unchanged edaravone will be log transformed prior to statistical analysis. For period 1 to 4, the analysis will be by analysis of variance (ANOVA) taking account of meal conditions. Factors accounting for the following sources of variation: sequence, subjects nested in sequences, periods, and meal conditions. For subjects having each value with fasted and period 5, the analysis will be by ANOVA taking account of meal conditions. Factors accounting for the following sources of variation: sequence, subjects nested in sequences, and meal conditions. Difference in least square (LS) means and corresponding 90% CI will be back transformed to obtain the estimate and CI of geometric mean ratio of each meal condition to fasted. As reference, the same analysis will also be on sulfate conjugate and glucuronide conjugate.

For C_{max} , and $AUC_{0-\infty}$ spaghetti plots will be produced showing individual differences between fasted condition and each meal condition.

9. DATA PRESENTATION CONVENTIONS

9.1. Number of Digits to Report

(1) Non-PK related

Statistic	Specification	Apply to
Minimum, Maximum	Same number of DPs as the data provided in the datasets	All original (i.e. non-derived)
	see section 7.3	All derived data
Mean, Median, SD, SE, Confidence intervals	One more DP than above	All
Percentages ^{*1}	1 DP	All

*1 Percentages: use 1 place beyond the decimal point, except for the following cases:

If the percentage is equal to 0, then leave blank, do not use (0)

If the percentage is equal to 100, then use "(100)" without a decimal

(2) PK Plasma Concentration

Statistic	Specification
Individual value	With the number of DPs to which they are reported
Mean, SD, Minimum, Median, Maximum	Same number of DPs as the individual value

(3) PK Parameters

Plasma PK Parameters

Statistic	Specification
Individual value	C_{max} : same number of DPs as the plasma concentration t_{max}^* : 2 DPs Kel: 4 DPs Other parameters to be summarized: number of DPs which the number of significant digits of a minimum parameter is three $AUC\%_{ex}$: 2 DPs Adjusted R^2 : 2 DPs Number of Kel points: 0 DP Lower and Upper limited of Kel: 2 DPs
Mean, SD, Minimum, Maximum, Median, Geometric mean	Same number of DPs as the individual values
CV%, Geometric CV%	1 DP
Ratios	3 DPs

*: t_{max} will be expressed basically in terms of median and range

Urine PK Parameters

Statistic	Specification
Individual value	$Ae, Ae\%$: 3 DPs

	CLR: number of DPs which the number of significant digits of a minimum parameter is three
Mean, SD, Minimum, Maximum, Median, Geometric mean	For Unchanged Edaravone: 3 DPs For Sulfate Conjugate: 2 DPs For Glucuronide Conjugate: 1 DP For Sum of Unchanged Edaravone and Metabolites: 1 DP
CV%, Geometric CV%	1 DP

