toxic dose in rats; however, these changes were relieved or disappeared after withdrawal from the drug. In dogs, salivation, sedation, blinking, sneezing, and hind limb weakness were observed in a transient manner.

In a 2-week multiple oral dose study, the NOAEL was 300 mg/kg/day in rats, 30 mg/kg/day in female dogs, and 100 mg/kg/day in male dogs. In rats, toxicological changes were observed only in the 1,000 mg/kg/day group, and were similar to those seen after rapid IV injection. Forestomach erosion, prolonged activated partial thromboplastin time, and submandibular gland acinar cell hypertrophy were observed as toxicological changes after an oral dose but not after rapid IV injection. In dogs, toxicological changes were observed in females in the ≥ 100 mg/kg/day groups and males in the 300 mg/kg/day group, and were similar to those seen after rapid IV injection.

In a 24-hour continuous IV administration study in dogs, neurologic manifestations (e.g., limited limb movement, muscle hypotonia) were observed in the 14-day 120 and 300 mg/kg/day groups, with the earliest onset shown on Day 12 of administration. Histopathological manifestations were peripheral and spinal nerve fiber degeneration. The NOAEL in neurotoxicity was 300 mg/kg/day for 5-day administration, 120 mg/kg/day for 10-day administration, and 60 mg/kg/day for 14-day administration. In a regimen of 5-day administration followed by 4-week interruption in the 24-hour continuous IV administration study in dogs, it has been indicated that the manifestations in the peripheral nerve tissue may be reversible due to the interruption.

At the NOAEL, there were no findings of clinical importance in other toxicity studies, as well.

The PK assessment in rats showed that AUC correlated well with the dose for IV administration. Edaravone was metabolized fast. The major metabolites were glucuronide conjugate and sulfate conjugate, which were excreted in the urine. The urinary excretion of the unchanged drug was approximately 1% of the dose. Regarding the sulfate conjugate and glucuronide conjugate, neither a radical scavenging effect nor a lipid peroxidation inhibitory effect have been observed.

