In an in vitro assay using human kidney homogenates, after deconjugation of the sulfate conjugate, edaravone was suggested to be reconjugated with glucuronic acid and excreted mainly as the glucuronide conjugate in the urine. Multiple uridine diphosphate glucuronyl transferases (UGTs), including UGT1A9 were involved the glucuronidation reaction. Edaravone was bound to human serum proteins at a ratio of 91% to 92% (primarily to albumin).

Edaravone increased mRNA expression of CYP1A2, CYP2B6, and CYP3A4 in human hepatocytes, indicating its inducing effect on P-450 isozymes. Both direct and time-dependent inhibitory effects of edaravone were strongest on CYP2C9 among each P-450 molecular species in human hepatic microsomes, with IC_{50} of 84.5 μ mol/L and 44.8 μ mol/L (shifted IC_{50}), respectively. Edaravone, its sulfate conjugate, and its glucuronide conjugate showed no inhibitory effects on metabolic activities of UGT1A1 and UGT2B7 in human hepatic microsomes. Edaravone showed an inhibitory effects on breast cancer resistance protein (BCRP) and organic anion transporter 3 (OAT 3), both of which are drug transporters, with IC_{50} of 121 μ mol/L and 72.3 μ mol/L, respectively. Edaravone sulfate conjugate showed OAT1 and OAT3 inhibitory effects with IC_{50} of 13.6 μ mol/L and 2.74 μ mol/L, respectively.

2) Clinical Study Results

Thus far, the following clinical studies of edaravone (injection) have been performed: 7 clinical pharmacology studies in healthy adult subjects in Japan and Europe; 8 clinical studies

Confidential

in patients with acute phase of cerebral infarction in Japan, Europe, and South Korea; 3 clinical studies in patients with subarachnoid hemorrhage in Japan; 5 clinical studies in patients with ALS in Japan; 1 clinical pharmacology study in patients with mild or moderate renal dysfunction in Japan; and 1 clinical pharmacology study in patients with mild or moderate hepatic dysfunction in Japan.

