10.1 Pharmacokinetics

Plasma and urine concentrations of unchanged edaravone, sulfate conjugate and glucuronate conjugate will be measured to calculate AUC_{0-t} , AUC_{0-24} , $AUC_{0-\infty}$, C_{max} , t_{max} , $t_{1/2}$, Kel , MRT , * CL/F , * V_z/F , * V_{ss}/F , * Ae , $Ae\%$, and CL_r/F by non-compartmental analysis (*: calculate only for unchanged edaravone). The detailed calculation method for each parameter will be described in the Statistical Analysis Plan.

The drug concentration measurement site will separately create a protocol for concentration measurement by the start of measurement and perform measurement according to it. The site will create a measurement result report.

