8.3.5. Physical Examinations	23
8.4. Pharmacokinetics Evaluation.....	23
8.4.1. Concentrations and Pharmacokinetic Parameters for unchanged edaravone, sulfate conjugate, and glucuronide conjugate	24
8.4.2. Analysis of Food Effect.....	24
9. DATA PRESENTATION CONVENTIONS	25
9.1. Number of Digits to Report	25
9.2. Treatments to Report.....	26
9.3. Analysis Visits to Report	26
10. CHANGE FROM THE PROTOCOL	27
11. SOFTWARE.....	27
12. REFERENCES	27

ABBREVIATIONS

Abbreviations	Definitions
AE	adverse event
ALT	alanine transaminase
ALP	alkaline phosphatase
AST	aspartate transaminase
ATC	anatomical therapeutic chemical
BLQ	below limit of quantification
BMI	body mass index
CI	confidence interval
CV	coefficient of variation
DP	decimal places
DRM	data review meeting
ECG	electrocardiogram
MedDRA	medical dictionary for regulatory activities
PK	pharmacokinetics
PT	preferred term
SAP	statistical analysis plan
SAE	serious adverse event
SAF	safety population
SD	standard deviation
SOC	system organ class
WHO	World Health Organization

LIST OF PK PARAMETERS

Parameters	Definitions
AUC_{0-24}	Area under the plasma concentration-time curve from zero up to 24 hour
AUC_{0-t}	Area under the plasma concentration-time curve from zero up to the last quantifiable concentration time point
$AUC_{0-\infty}$	Area under the plasma concentration-time curve from zero up to infinity with extrapolation of the terminal phase
$AUC\%_{ex}$	Area under the (plasma) concentration-time curve extrapolated from the last quantifiable concentration time point to infinity in % of the total $AUC_{0-\infty}$
Ae_{0-24}	Cumulative urinary excretion amount of drug from zero to 24 hour
Ae_{0-48}	Cumulative urinary excretion amount of drug from zero to 48 hour
C_{max}	Maximum plasma concentration after administration
C_{last}	Last quantifiable concentration
CL/F	Apparent total clearance
CL_r	Renal clearance
Kel	Elimination rate constant from the central compartment
$LLOQ$	Lower limit of quantification
LOQ	Limit of quantification
MRT	Mean residence time
NC	Not calculated
$t_{1/2}$	Terminal elimination half-life in plasma concentration-time course
V_{ss}/F	Apparent volume of distribution at steady state
V_z/F	Apparent volume of distribution during terminal phase
$Ae\%$	Urinary excretion ratio of drug

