2.2.2. Pharmacokinetics Assessments

- (1) Drug concentration (in plasma and urine)
Unchanged edaravone, sulfate conjugate, and glucuronide conjugate
- (2) Pharmacokinetic parameters
Unchanged edaravone: AUC_{0-24} , AUC_{0-t} , $AUC_{0-\infty}$, C_{max} , t_{max} , $t_{1/2}$, Kel, MRT, CL/F, V_z/F , V_{ss}/F , Ae, Ae%, CLr
Sulfate conjugate and glucuronide conjugate: AUC_{0-t} , AUC_{0-24} , $AUC_{0-\infty}$, C_{max} , t_{max} , $t_{1/2}$, Kel, Ae, Ae% (t: Final concentration measurable time point)
Other PK parameters (for all PK profiles for which the Kel has been calculated): $AUC\%_{ex}$, Adjusted R^2 , Number of Kel points, Lower limit of Kel, Upper limit of Kel

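### Does dividing Ae by dose overstate urinary recovery of the edaravone conjugates and of the summed recovery?

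*SAP*

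**What the plan says.** SAP Appendix 1 has a single row for Ae, in mg, formed as concentration in urine times urine volume. It has a single row for Ae%, with unit %, formed as Ae / Dose. Neither row is split by analyte and neither contains a molecular weight. The SAP's parameter list describes Ae% only as "Urinary excretion ratio of drug".

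SAP 2.2.2 measures unchanged edaravone, "sulfate conjugate, and glucuronide conjugate" in plasma and urine, and asks for Ae and Ae% for all three. Renal clearance is listed for unchanged edaravone alone. The dose throughout is 105 mg of edaravone (Protocol 7.1 and 8.3).

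SAP 9.1, in the table of digits for urine parameters, includes the line "For Sum of Unchanged Edaravone and Metabolites: 1 DP". SAP 8.4.1 states: "The PK parameters listed in Section 2.2.2 will be calculated for each subject using non-compartmental model". The sum is not in that list and has no row in Appendix 1.

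Protocol 10.1 divides the work in two. On calculations it says "The detailed calculation method for each parameter will be described in the Statistical Analysis Plan". On the assay it says "The drug concentration measurement site will separately create a protocol for concentration measurement by the start of measurement".

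**The concern.** A conjugate is edaravone with a group attached, so a given number of molecules weighs more as conjugate than as parent drug. If the laboratory reports milligrams of conjugate, dividing by milligrams of edaravone dose does not give a fraction of the dose. It gives something larger, and the three analytes cannot then be added on a common scale.

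The conjugates may also be the main part of what is recovered. Protocol section 1 (3), on non-clinical studies, says of rats: "The major metabolites were glucuronide conjugate and sulfate conjugate, which were excreted in the urine". On human kidney homogenates it suggests that edaravone is "excreted mainly as the glucuronide conjugate in the urine". If that carries over to these subjects, the analyte with the largest possible error would dominate the sum. A total recovery could look plausible and be wrong, or pass 100% of dose.

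The protocol promises that the SAP will give the calculation of each parameter, so silence on the basis looks like an omission in the document that should have covered it.

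**Working it through.** The documents give no Ae% result, no molecular weight and no human urinary recovery, so there is no figure of the plan's own to reproduce. The check has to be conditional.

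**Inputs from the documents:** dose 105 mg edaravone; Ae in mg; Ae% = Ae / Dose.

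**Inputs assumed:** parent molecular weight (MW) 150 to 300; sulfation adds 80.06 and glucuronidation 176.12; glucuronide is 60% to 90% of excreted conjugate; true recovery as conjugates 40% or 60% of dose.

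**1. Direction.** For a conjugate, reported Ae% / true Ae% = MW(conjugate) / MW(parent) if concentrations are conjugate mass. This exceeds 1 for any parent weight. If concentrations are edaravone equivalents, the ratio is exactly 1.

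**2. Size per analyte, conjugate-mass case.**

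| Parent MW | Sulfate factor | Glucuronide factor |
|---|---|---|
| 150 | 230.06 / 150 = 1.53 | 326.12 / 150 = 2.17 |
| 200 | 280.06 / 200 = 1.40 | 376.12 / 200 = 1.88 |
| 250 | 330.06 / 250 = 1.32 | 426.12 / 250 = 1.70 |
| 300 | 380.06 / 300 = 1.27 | 476.12 / 300 = 1.59 |

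**3. Size for the two conjugates together,** if unconverted values are added.
- Low: 0.6 × 1.587 + 0.4 × 1.267 = 1.459.
- High: 0.9 × 2.174 + 0.1 × 1.534 = 2.110.
- True 40% would be shown as 58% to 84%, and true 60% as 88% to 127%. In mass, 0.60 × 105 = 63 mg becomes 63 × 1.459 = 92 mg up to 63 × 2.110 = 133 mg.
- The total passes 100% only when true recovery exceeds 100 / 2.110 = 47% to 100 / 1.459 = 69%.

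**4. The opposite error.** Suppose a molecular-weight term were written into Appendix 1 and the laboratory already reported edaravone equivalents. Conjugate Ae% would then be multiplied by 1 / 1.267 = 0.79 for the sulfate at one end and by 1 / 2.174 = 0.46 for the glucuronide at the other. Correcting without knowing the basis can do as much harm as not correcting.

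**5. Does the text select a basis?** The unit mg does not, because edaravone equivalents are also expressed in mg. The structure leans towards a shared basis: one formula, one dose as denominator and a planned total over three analytes are all correct as written if the values are edaravone equivalents. This is inference; the SAP does not say it.

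**6. What is the sum?** The line stands in the urine table. The only metabolites measured are the two conjugates, and renal clearance belongs to unchanged drug alone. That leaves Ae, Ae% or both, added over three named analytes. The missing items are a row and a basis.

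**7. Reach.** SAP 8.4.2 models log Cmax and AUCs in plasma. Protocol 13.4.2 extends the same log-scale comparison to other parameters for reference. For a single conjugate, a constant factor adds the same amount to every log value and cancels in the ratio of meal to fasted. The ratio of two sums need not cancel exactly. At equal true recovery, a shift in glucuronide share from 60% to 90% between conditions would move it by 1.555 / 1.459 = 1.07 at MW 300 (0.9 × 1.587 + 0.1 × 1.267 = 1.555) or by 2.110 / 1.918 = 1.10 at MW 150 (0.6 × 2.174 + 0.4 × 1.534 = 1.918). Neither document plans a test or a decision on the sum.

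**The case for a change.** The best case for a change is that the calculation from concentration to Ae% belongs in the SAP by the protocol's own statement. If no conversion is needed because of how the assay reports, Appendix 1 is the natural place to say so. Programming, checking and approval are spread over several parties (SAP 1), and a programmer who follows the row literally applies no conversion. Stating the basis would cost a line or two and need no new data. The sum lacks a formula whichever basis applies. The Ae% row also omits the multiplication by 100 that the row for the extrapolated AUC percentage shows.

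Much of this stands as a description. The SAP is less complete here than the protocol led the reader to expect. It does not stand as evidence of a wrong result. Whether the row is right depends on a laboratory document that is not available here, and under one ordinary reporting basis it is right as written. The parties computing Ae% receive the measurement results from the laboratory (Protocol 10.1 and 17.1), and must know what a concentration refers to before they can form an amount at all. SAP 6.3 records that the pharmacokinetic data had already been examined at the data review meeting before lock, so the people writing and using the plan had those data to hand. The absent factor of 100 is clerical, since the unit column says %.

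**Conclusion.** The textual observation is correct: one formula for three analytes, no stated reporting basis, and a sum that appears only as a rounding rule. It does not show that the plan produces a wrong number. The error is a factor of 1 under edaravone equivalents. It is 1.27 to 1.53 for the sulfate and 1.59 to 2.17 for the glucuronide only if concentrations are conjugate mass and no one converts them. Only the direction of that conditional error is secure; its size rests on assumed molecular weights, and the summed figures rest also on assumed excretion shares and recoveries.

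This is a gap that analysts fill sensibly, by reading the basis from the laboratory's report and adding like with like. Writing in a molecular-weight correction without that knowledge could create the opposite error. What is exposed is confined to descriptive secondary summaries of absolute conjugate recovery and their total. The primary plasma comparison, the urine results for unchanged drug and single-analyte meal ratios are untouched. No change to the plan is called for.

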9.2. Treatments to Report

Treatment	For TFLs
Dosing under fasted condition	Fasted
Dosing 8 hours after high-fat meal	8 hours after high-fat meal
Dosing 4 hours after low-fat meal	4 hours after low-fat meal
Dosing 2 hours after light meal	2 hours after light meal
Dosing 2 hours after low-fat meal	2 hours after low-fat meal

9.3. Analysis Visits to Report

(1) Non-PK related

Analysis Visit	Analysis Time Point	Apply to	Laboratory Tests	Vital Signs	12-Lead ECGs
Screening		X		X	X
Day -1		X (baseline)		X	X
Day 1	Pre-dose			X (baseline)	X (baseline)
Day 1	1 hour			X	X
Day 2	24 hours			X	X
Day 3	Pre-dose			X (baseline)	X (baseline)
Day 3	1 hour			X	X
Day 4	24 hours			X	X
Day 5	Pre-dose	X		X (baseline)	X (baseline)
Day 5	1 hour			X	X
Day 6	24 hours			X	X
Day 7	Pre-dose			X (baseline)	X (baseline)
Day 7	1 hour			X	X
Day 8	24 hours			X	X
Day 9	46 hours	X		X	X
Day 23		X		X	X
Day 24	Pre-dose			X (baseline)	X (baseline)
Day 24	1 hour			X	X
Day 25	24 hours			X	X
Day 26	48 hours	X		X	X
Follow up		X		X	X

Screening, unscheduled visits, retests (same visit number assigned) will not be displayed in by-visit summary tables, but will be included in the data listings.

10. CHANGE FROM THE PROTOCOL

There are currently no changes to analysis from protocol.

11. SOFTWARE

All statistical analyses will be performed using SAS version 9.4 or higher.

The PK parameters will be calculated using WinNonlin® software (version 6.3 or later).

Appendix 1 Pharmacokinetic Parameter Calculations

- Actual blood sampling times will be used in the calculation of pharmacokinetic parameters
- All concentrations below the LLOQ will be set at zero for pharmacokinetic calculations
- When K_{el} is missing (or cannot be determined), $t_{1/2}$, $AUC_{0-\infty}$, $AUC\%_{ex}$, CL/F , MRT , V_z/F and V_{ss}/F will not be calculated.

PK Parameter Calculations		
Parameters	Unit	Calculation
C_{max}	ng/mL	will be determined by visual inspection
$AUC_{0-\infty}$	ng·h/mL	$AUC_{0-\infty} = AUC_{0-t} + C_{last} / K_{el}$ C_{last} : last measurable concentration
$AUC\%_{ex}$	%	$AUC\%_{ex} = (AUC_{0-\infty} - AUC_{0-t}) / AUC_{0-\infty} \times 100$
AUC_{0-t}	ng·h/mL	will be calculated using the linear trapezoidal method and actual times $AUC_{0-t} = \sum_{i=1}^n \frac{t_i - t_{i-1}}{2} (C_{i-1} + C_i)$
AUC_{0-24}	ng·h/mL	will be calculated using time until 24 h drug concentration
t_{max}	h	Measured time of C_{max}
$t_{1/2}$	h	$t_{1/2}$ will be determined as: $t_{1/2} = \log_e (2) / K_{el}$
K_{el}	1/h	
The exponential rate constant of the terminal phase, K_{el}, will be estimated by log-linear regression, if determinable. The number of data points included in the regression will be determined by visual inspection. Wherever possible, a minimum of 3 data points will be used in the estimation of K_{el}.
 
During the analysis, this calculation method repeats regressions using the last three points with non-zero concentrations, then the last four points, last five, etc. The time of maximum concentration (t_{max}) will be excluded from the estimation of K_{el}.
 
Points with a value of zero for the dependent variable are excluded. For each regression, an adjusted R^2 is computed
 $Adjusted R^2 = 1 - \frac{(1 - R^2) \times (n - 1)}{(n - 2)}$ 
where n is the number of data points in the regression and R^2 is the square of the correlation coefficient.

		
The regression with the largest adjusted R^2 is selected to estimate Kel, with these caveats:
 
 - If the adjusted R^2 does not improve, but is within 0.0001 of the largest adjusted R^2 value, the regression with the larger number of points is used. - Kel must be positive, and calculated from at least three data points.
CL/F	L/h	$CL/F = \frac{\text{Dose}}{AUC_{0-\infty}}$
MRT	h	$AUMC_{0-\infty} = \sum_{i=1}^n \frac{(t_i - t_{i-1})(t_i \times C_i + t_{i-1} \times C_{i-1})}{2} + \frac{t \times C_t}{Kel} + \frac{C_t}{(Kel)^2}$ $MRT_{0-\infty} = \frac{AUMC_{0-\infty}}{AUC_{0-\infty}}$
V_z/F	L	$V_z/F = CL/F \times \frac{1}{Kel}$
V_{ss}/F	L	$V_{ss}/F = MRT \times CL/F$
Number of Kel points	—	will be determined using number of points used in computing Kel. If Kel cannot be estimated, zero.
Lower Limit of Kel	h	will be determined using lower limit on time to be included in the calculation of Kel
Upper Limit of Kel	h	will be determined using upper limit on time to be included in the calculation of Kel
Ae	mg	urine concentration \times urine volume
Ae%	%	Ae / Dose
CLr	L/h	$CLr = \frac{Ae}{AUC_{0-\infty}}$
